8.3.2. Method of Detecting AEs and SAEs

Care will be taken not to introduce bias when detecting AEs and SAEs. Open-ended and nonleading verbal questioning of the subject is the preferred method to inquire about AE occurrences.

At each visit, subjects will be queried regarding any AEs that have occurred since the last visit. Subjects will be asked to volunteer information concerning AEs with a nonleading question such as, "How do you feel?" Study site personnel will then record all pertinent information. The study treatment compliance record should also be reviewed to detect potential intentional or unintentional overdoses.

Any AEs identified in the subject diaries will be reported in the appropriate electronic case report form (eCRF) module, and if SAEs, as described in Section 10.3.

8.3.3. Follow-up of AEs and SAEs

After the initial AE/SAE report, the investigator is required to proactively follow each subject at subsequent visits/contacts. All nonserious AEs must be followed until resolution or until the last study visit whichever comes first; except for subjects who withdraw early from the study for whom nonserious AEs will be followed until resolution or for 28 days after the last administration of study treatment, whichever comes first.

All SAEs and nonserious AESIs will be followed to resolution, stabilization, the event is otherwise explained, or until follow-up is no longer possible. Further information on follow-up procedures is provided in Section 10.3.

8.3.4. Regulatory Reporting Requirements for SAEs

Prompt notification by the investigator to the sponsor of an SAE is essential so that legal obligations and ethical responsibilities regarding the safety of the study treatment under clinical investigation are met.

The sponsor has a legal responsibility to notify both the local regulatory authority and other regulatory agencies about the safety of the study treatment under clinical investigation. The sponsor will comply with country-specific regulatory requirements regarding safety reporting to regulatory authorities, IRBs/IECs, and investigators.

Investigator safety reports must be prepared for suspected unexpected serious adverse reactions (SUSARs) according to local regulatory requirements and sponsor policy, and forwarded to investigators as necessary.

An investigator who receives a SUSAR (IND Safety Report) describing an SAE or other specific safety information (ie, summary or listing of SAEs) from the sponsor will review and then file it

with the Investigator's Brochure, and will notify the IRB/IEC, if appropriate according to local requirements.

8.3.5. Pregnancy

All subject pregnancies that are identified during or after this study, where the estimated date of conception is determined to have occurred at any time during the study or (within 28 days of the last study treatment for those who terminate early) must be reported, followed to conclusion, and the outcome reported, even if the subject is withdrawn from the study. Pregnancies that occur in the partner of a treated subject (ie, female partner of male subject) also must be reported. The investigator must report (as outlined above) all pregnancies within 24 hours using the Pregnancy Report Form. Monitoring of the pregnancy should continue until conclusion, and follow-up information detailing the progress and outcome must be submitted on 1 or more Pregnancy Report Forms. A Two-Month Follow-up Pregnancy Report Form detailing the status of the infant must also be submitted.

Pregnancy itself is not regarded as an AE unless there is suspicion that the investigational product under study may have interfered with the effectiveness of a contraceptive medication. Likewise, elective abortions without complications are not considered AEs. Any SAEs associated with pregnancy (eg, congenital abnormalities/birth defects, or any other serious events) must additionally be reported as such using the Serious Adverse Event (SAE)/Reportable Event Form (see Section 10.3). Spontaneous miscarriages should also be reported and handled as SAEs.

Subjects will be instructed to immediately notify the investigator of any pregnancies.

A subject who becomes pregnant must be immediately discontinued from study treatment but may remain in the study (see Section 7.1). Should a subject discontinue study treatment due to pregnancy, alternative treatment (if available) should be arranged according to standard of care, as determined by the investigator. Attempts to obtain the pregnancy follow-up and pregnancy outcome information detailed above are necessary even if a subject withdraws from the study because of pregnancy.

8.3.6. AEs/SAEs Experienced by Nonsubjects Exposed to Study Treatment

Nonsubjects are persons who are not enrolled in the study but have been exposed to study treatment, including instances of diversion of study treatment. Any AEs/SAEs occurring in nonsubjects from such exposure will be reported to the Endo PVRM Department (when the nonsubject agrees) on the Serious Adverse Event (SAE)/Reportable Event Form regardless of whether the event is serious or not. Instructions for completing the form for events experienced by nonsubjects will be provided. SAEs occurring in nonsubjects exposed to study treatment will be processed within the same SAE reporting timelines as described in Section 10.3. Additionally, the treatment accountability source documentation at the site should reflect this occurrence.

8.3.7. Adverse Events of Special Interest

AESIs for this study include:

• Bruising, ecchymosis, hematomas, and contusions that occur remote to the site of treatment administration.

• Any hypersensitivity reactions.

These events will be reported as AEs in the eCRF. All AESIs will be evaluated for seriousness and severity. If any of these events meet the criteria for an SAE, they will also be reported as such using the procedure outlined in Section 10.3.

8.4. Overdose

Study treatment overdose is any accidental or intentional use of treatment in an amount higher than the dose indicated by the protocol for that subject. Study treatment compliance should be reviewed to detect potential instances of overdose (intentional or accidental).

Any treatment overdose during the study should be noted on the study treatment eCRF.

An overdose is not an AE per se, however all AEs associated with an overdose should both be entered on the AE eCRF and reported using the procedures detailed in Section 10.3, even if the events do not meet seriousness criteria. If the AE associated with an overdose does not meet seriousness criteria, it must still be reported using the Endo Serious Adverse Event (SAE)/Reportable Event Form and in an expedited manner, but should be noted as nonserious on the form and the AE eCRF.

8.4.1. Study Treatment Abuse/Misuse

AEs associated with misuse or abuse will be appropriately reported as AEs or SAEs, and monitored per Section 10.3.

8.5. Pharmacokinetics

Not applicable.

8.6. Pharmacodynamics

Not applicable.

8.7. Genetics

Not applicable.

8.8. Biomarkers

8.8.1. Immunogenicity Assessments

Serum samples will be collected at times outlined in the Schedule of Activities and will be tested for binding anti-AUX-I and anti-AUX-II antibody testing. When immunogenicity samples are required on a Treatment Day, the sample will be collected prior to study treatment administration. The antibody-positive samples also will be tested for neutralizing antibodies.

The serum samples obtained will be processed, stored and then shipped frozen on dry ice to Endo's appointed laboratory for the determination of anti-AUX-I and anti-AUX-II antibodies. Specific instructions for the collection, processing, storage, handling, and shipment of the immunogenicity samples will be provided in the Study Operations Manual.

De-identified immunogenicity samples may be stored for a maximum of 5 years (or according to local regulations) following the last subject's last visit for the study at a facility selected by the sponsor to enable further analysis of immune responses to study treatment; develop methods, assays, prognostics and/or companion diagnostics related to specify the treatment target, disease process, pathways associated with disease state, and/or mechanism of action of the study treatment.

8.9. Medical Resource Utilization and Health Economics

Not applicable.

9. STATISTICAL CONSIDERATIONS AND METHODS

9.1. Sample Size Determination

A post hoc analysis was conducted using a subgroup of AUX-CC-871 subjects who were rated with moderate/severe AC based on baseline MRI images. This subgroup displayed a notable treatment effect (EN3835 vs placebo) on the pain and composite components of the adapted ASES questionnaire. This subgroup also displayed a treatment effect trend for the functional component of the adapted ASES. Given this result, the sample size calculation is based on the mean and SD found in this subgroup for the adapted ASES composite score on Day 95. Given a mean change from baseline value of 38.6 for the EN3835 group and 27.6 for the placebo group with an SD of 21.6, a sample size of approximately 142 subjects would be required given a 1:1 randomization and a type I error of 0.05 with a power of 85%. With an expected drop-out rate of approximately 20%, 180 subjects (90 EN3835 and 90 placebo) should be dosed to ensure 142 subjects complete the study.

9.2. **Populations for Analysis**

For the purposes of analysis, the following populations are defined:

- The Safety Population is defined as all randomized subjects who received at least 1 injection of study treatment (EN3835 or placebo). All safety analyses will be based on this population.
- The Intent-to-Treat (ITT) Population is defined as all randomized subjects who received at least 1 injection of study treatment (EN3835 or placebo).
- The Modified Intent-to-Treat (mITT) Population is defined as all ITT subjects who have a valid baseline adapted ASES composite score in the affected shoulder and at least 1 valid adapted ASES composite score after the injection of the study treatment. All efficacy analyses will be based on this population.
- The Per-Protocol (PP) Population is defined as those subjects in the mITT Population who do not have any major protocol deviations. Determination of PP subjects will be completed before the study database is closed and locked. If more than 10% of the mITT Population is excluded from the PP Population, then all efficacy summaries will be repeated using the PP Population for the sensitivity analysis.

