2.3. Benefit/Risk Assessment

Although a thorough benefit of EN3835 has not been fully established in the treatment of AC, the post hoc analyses from the previous phase 2b study (AUX-CC-871) and previous AC studies indicate that EN3835 should be further explored as a treatment. In addition, the lack of consensus regarding treatment of AC and the risks associated with surgical or drug treatment or with long-term corticosteroid use suggest that safe and effective treatments for this condition are needed.

In the most recent study of EN3835 in AC (AUX-CC-871), the most common (\geq 5% of subjects) treatment-related, treatment-emergent adverse events (TEAEs) were musculoskeletal pain (34.2%), contusion (28.7%), injection site pain (21.1%), ecchymosis (19.8%), injection site bruising (19.4%), localized edema (8.0%), and pruritus (5.1%). These events are similar to events reported in the clinical trials of EN3835 for the approved indications, and postmarketing safety data are consistent with the safety data reported in clinical trials.

Use caution when administering EN3835 so as not to inject intra-articularly. A single animal study indicated significant adverse events associated with intra-articular injection of EN3835. While the effect in humans is not known, intra-articular injection (misapplication) of EN3835 during treatment of AC must be avoided.

More information about the known and expected benefit, risks, and reasonably expected adverse events (AEs) can be found in the Investigator's Brochure (Endo, 2020).

Risks associated with the use of a local anesthetic include bruising, pain, tingling, blurred vision, dizziness, headache, muscle twitching, weakness, and continuing numbness. Local anesthetics can sometimes cause allergic reactions including hives, itching, and difficulty breathing. In rare cases, cyanosis can occur at the site of injection; and very rarely, use of a local anesthetic can lead to depressed central nervous system syndrome.

The baseline shoulder X-ray exposes subjects to a very low level of radiation. Extensive exposure to radiation can lead to cancer. Exposure to any radiation can harm an unborn fetus in a pregnant woman.

Risks associated with ultrasound are rare; however, subjects undergoing ultrasound may experience slight heating of tissues and the creation of cavitations (small pockets of gas) within the body. The long term effects of these events are unknown.

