4. STUDY DESIGN

4.1. Overall Design

This study is a Phase 2b, double-blind, placebo-controlled study of the safety and efficacy of EN3835 for the treatment of AC of the shoulder. To be eligible for treatment, a subject must have unilateral idiopathic AC of the shoulder with restricted ROM and function in the affected shoulder. Subjects will be screened for study eligibility within 28 days before the first injection of study treatment. Approximately 180 subjects will be randomly assigned to EN3835 or placebo so that approximately 142 evaluable subjects will complete the study.

During screening subjects will undergo MRIs of both shoulders. These images will be reviewed through a central blinded read to determine subject eligibility (that each subject has AC without confounding pathologies). Following screening, eligible subjects will be randomized 1:1 to receive EN3835 0.58 mg/1 mL or volume matched placebo. EN3835 or placebo will be administered by ultrasound-guided injection at the injection site

following the administration of a local anesthetic. Subjects will receive up to 3 injections of study treatment (total dose: 1.74 mg) separated by a minimum of 21 days. Following each injection, subjects will remain under observation for at least 30 minutes. All subjects will undergo standardized, supervised, in-office PT sessions after each treatment visit. In addition, subjects will complete standard home exercises starting 3 days after each injection of study treatment through the Day 95 Visit. Subjects will be evaluated for shoulder ROM, AC severity, function, and pain at each subsequent study visit. Dosing may be withheld at the Day 22 and 43 Visits if functional parameters are met. Subjects will be expected to complete all study visits, even if they do not receive study treatment at the Day 22 and/or Day 43 Visits. Follow-up visits will be conducted approximately 64 and 95 days after the first dose of EN3835 or placebo.

An interim analysis for safety and futility is planned for when approximately 86 subjects have completed the Day 95/Early Termination Visit. Enrollment will continue during this analysis.

22 October 2021

The duration of the study from first subject first visit to last subject last visit will be dependent on the ability of the sites to identify and enroll eligible subjects. The study is expected to screen subjects over approximately 12 months. The entire study is expected to require approximately 18 months to complete.

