5.2. Subject Exclusion Criteria

A subject is ineligible for study participation if, at the Screening Visit and/or on Day 1, the subject:

- 1. Has a known allergy to collagenase or any other excipient of EN3835 or any other procedural medication (including local anesthetics).
- 2. Has received treatment for AC (in the timeframes outlined below) or is planning to receive any treatment (other than study treatment) for AC at any time during the study in the affected shoulder, including but not limited to:
 - PT or acupuncture within 2 weeks before the first injection of study treatment.
 - Intra-articular or intrabursal injections of lidocaine, suprascapular nerve blocks, or electroanalgesic and/or thermoanalgesic modalities within 1 month before the Screening Visit.
 - Intra-articular or intrabursal injections of corticosteroids within 8 weeks before the Screening Visit.
 - Intra-articular or intrabursal injections of sodium hyaluronate and/or glenohumeral distension arthrography within 3 months before the Screening Visit.
 - MUA at any time prior to the study.
 - Surgery (including arthroscopic or open capsular release, capsulectomy, or capsulotomy) at any time prior to the study.

- 3. Has any abnormalities/conditions in the affected shoulder that would be potentially confounding to the evaluations of efficacy as determined by the central MRI review committee grading criteria. The shoulder pathologies to be assessed include but are not limited to the following:
 - AC as a result of traumatic injury (ie, direct injury to the shoulder such as fracture of the humerus or clavicle immediately preceding the onset of this episode of AC). Traumatic events in the past that are not temporally related to the onset of this episode of AC would not necessarily exclude a subject from participating in the study.
 - Active subacromial impingement (subacromial/subdeltoid bursitis, decreased subacromial space, or bursal sided fraying).
 - Calcified tendonitis.
 - Glenohumeral joint arthrosis.
 - Glenohumeral joint inflammatory arthropathy.
 - Rotator cuff tears (supraspinatus, infraspinatus, teres minor, or subscapularis).
 - Fracture (humerus, glenoid, or clavicle).
 - Acromioclavicular arthropathy.
 - Biceps tendon pathologies.
 - Bursitis.
 - Labral tears/suspected labral tears.
 - Bone pathologies.
- 4. Has a prosthesis or replacement of right or left shoulder, elbow, wrist, and/or hand.
- 5. Has any of the following systemic conditions:

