6.3. Measures to Minimize Bias

Subjects will be randomized according to a validated computer-generated allocation scheme to receive the study treatment described above in a 1:1 ratio using an interactive response technology (IRT) system. Subjects, investigators, site personnel, and Endo personnel (except clinical supplies personnel) will be blinded to treatment assignment.

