3.5. Determination of Sample Size

A post hoc analysis was conducted using a subgroup of AUX-CC-871 subjects who were rated with moderate/severe AC based on baseline MRI images. This subgroup displayed a notable treatment effect (EN3835 vs placebo) on the pain and composite components of the adapted ASES questionnaire. This subgroup also displayed a treatment effect trend for the functional component of the adapted ASES. Given this result, the sample size calculation is based on the mean and SD found in this subgroup for the adapted ASES composite score on Day 95. Given a mean change from baseline value in adapted ASES composite score at Day 95 of 38.6 for the EN3835 group and 27.6 for the placebo group with an SD of 21.6, a sample size of approximately 142 subjects would be required given a 1:1 randomization and a type I error of

0.05 with a power of 85%. With an expected drop-out rate of approximately 20%, 180 subjects (90 EN3835 and 90 placebo) should be dosed to ensure 142 complete the study.

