3.15.7. Magnetic Response Imaging (MRI) and X-rays

An X-ray of the affected shoulder is required at screening unless there is a historic X-ray of the affected shoulder that was taken within 30 days of the Screening Visit.

MRIs of the affected shoulder will be performed for all subjects at Screening and Day 95 and of the contralateral shoulder at the Screening Visit only.

Subjects should complete all other screening activities prior to the MRIs required at screening and must meet the entry criteria.

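### Does the 85% power need qualifying because its 11-point effect comes from a post hoc MRI-severity subgroup?

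*Protocol*

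**What the plan says.** Protocol 9.1 and SAP 3.5 plan on mean changes of 38.6 and 27.6 and an SD of 21.6. They name the source as a "subgroup of AUX-CC-871 subjects who were rated with moderate/severe AC based on baseline MRI images" and call the analysis post hoc. Protocol 9.1 then states that "the sample size calculation is based on the mean and SD found in this subgroup for the adapted ASES composite score on Day 95". SAP 3.5 gives the reason for using it: "This subgroup displayed a notable treatment effect (EN3835 vs placebo) on the pain and composite components of the adapted ASES questionnaire". The result is about 142 subjects for 85% power at a type I error of 0.05, with 180 dosed to allow for about 20% drop-out.

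Protocol 2.3 is candid about the evidence. It says the benefit is not fully established and that "the post hoc analyses from the previous phase 2b study (AUX-CC-871) and previous AC studies indicate that EN3835 should be further explored".

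In the present trial the central MRI read is used "to determine subject eligibility (that each subject has AC without confounding pathologies". Exclusion criterion 3 covers conditions "potentially confounding to the evaluations of efficacy as determined by the central MRI review committee grading criteria". The severity-type entry thresholds in Protocol 5.1 are clinical: at least 30% loss of passive external rotation and a function subscale score below 35. On allocation, Protocol 6.3 says only this: "Subjects will be randomized according to a validated computer-generated allocation scheme to receive the study treatment described above in a 1:1 ratio". The primary model in SAP 7.9.1.1 has treatment, visit and their interaction, fitted in the mITT Population. The baseline outputs in SAP 4.3, 7.3, 7.5, 7.7 and 7.8 list no MRI severity, although "MRIs of the affected shoulder will be performed for all subjects at Screening and Day 95".

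**The concern.** The planning effect was chosen from subjects selected on MRI severity after the data were seen, and it is applied without discount to subjects who, as far as the text shows, are not selected that way. If milder cases respond less, the average effect is below 11 points and the real power is below 85%. The plan neither states this condition nor gives a sensitivity range.

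At stake is how a non-significant result would be read. Without the severity mix, a reader could not tell whether the 11-point hypothesis failed in the kind of subject it came from or was averaged over others. The severity question might then be taken up post hoc a second time.

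**Working it through.** **Inputs.** Difference 38.6 − 27.6 = 11.0; SD 21.6; 1:1 allocation; alpha 0.05; power 85% (Protocol 9.1, SAP 3.5). Two-sided testing is from SAP 6.1.

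**Reproducing the plan's figure.** The normal approximation gives n per arm = 2 × (1.960 + 1.036)² × (21.6/11.0)² = 69.2, so 70 per arm, 140 in all. With the two-sample t test (noncentral t, 2n − 2 degrees of freedom, noncentrality = difference / [21.6 × √(2/n)]), power is 84.9% at 70 per arm. At 71 per arm the standard error is 3.63, the noncentrality 11/3.63 = 3.03 and power 85.4%. So 142 is right. For drop-out, 142/0.80 = 177.5, so 178 against the stated 180.

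**How far power depends on the average effect.** The effects below are an assumed range, since the documents give no all-subject difference from placebo in AUX-CC-871. The column for 90 per arm is a ceiling, reached only if every dosed subject contributes fully; the mITT Population does include early terminators.

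| Average effect | 71 per arm | 90 per arm |
|---|---|---|
| 12 | 90.8% | 96.0% |
| 11 | 85.4% | 92.5% |
| 10 | 78.2% | 87.1% |
| 9 | 69.3% | 79.4% |
| 8 | 59.2% | 69.5% |

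The effect needed for 80% power is 10.2 points at 71 per arm and 9.1 at 90. The SD matters in both directions: at 11 points and 71 per arm, SD 20 gives 90.2% and SD 23 gives 80.8%.

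Dilution can be sketched as average effect = share × 11 + (1 − share) × effect in the others, with share and remainder effect both assumed. With 80% moderate/severe and no effect in the rest, the average is 8.8 points and power at 71 per arm is 67.4%. With half the effect (5.5) in the rest, the average is 9.9 and power 77.4%.

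**What the primary analysis shows.** SAP 7.9.1.1 reports the EN3835 minus placebo difference with a 95% CI. A two-sample approximation to its half-width is t(0.975, 2n − 2) × 21.6 × √(2/n):
- 71 per arm: 1.977 × 3.625 = 7.2 points.
- 90 per arm: 1.973 × 3.220 = 6.4 points.

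At 71 per arm an observed difference below 11 − 7.2 = 3.8 points would exclude 11. One between 3.8 and 7.2 would be non-significant yet compatible with 11. The interval makes that distinction whatever the planned power was.

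**What severity-stratum estimates would show.** Take assumed shares of 80% or 60% moderate/severe. With a and b subjects per arm in the two strata, the contrast between stratum effects has half-width t(0.975, 2n − 4) × 21.6 × √(2/a + 2/b).

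| Per arm, share | Moderate/severe stratum | Contrast between strata |
|---|---|---|
| 71, 80% (56.8 and 14.2) | 8.0 | 17.9 |
| 71, 60% (42.6 and 28.4) | 9.3 | 14.6 |
| 90, 80% (72 and 18) | 7.1 | 15.9 |
| 90, 60% (54 and 36) | 8.2 | 13.0 |

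Every contrast half-width exceeds the 11-point effect itself. Even complete loss of effect in the milder subjects could not be reliably distinguished from none. The moderate/severe stratum alone, with no complement, says nothing about dilution.

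**The case for a change.** The best case for a change is that saying where a number came from is not the same as saying to whom it is meant to apply. The condition here is more specific than the usual dependence of power on an assumed effect: MRI severity defined the planning subgroup, yet nothing visible requires it or reports it. Post hoc selection is a good reason to suspect an optimistic effect. At 71 per arm a shortfall of one point already takes power below 80%. A sentence and a baseline row would cost almost nothing.

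Much of this stands as description. The condition is not spelled out and the visible outputs do not show the severity mix. Three things limit it.

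- A mismatch of populations is possible but not shown. The committee's grading criteria are not reproduced and could select on severity. The rotation and function thresholds and the exclusion of confounding pathology could preserve or raise the effect.
- The severity mix may be covered elsewhere. The exploratory objective and SAP 4.7.8 and 7.9.3.1 are blacked out, and MRI is repeated at Day 95 with no visible analysis. SAP 6.1 promises listings of all eCRF data, which would include a grade if one is held there. Table layouts are in a separate module (SAP 11). None of this proves coverage, but it prevents calling it an omission.
- The power table is generic. It would look the same for any two-arm trial with this sample size and SD, so it measures no defect in this one.

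**Conclusion.** No change is needed. The stated power and sample size are correct for the stated inputs, and the post hoc subgroup is named as their source in both documents. Applying its mean and SD to the planned sample leaves the assumption all but stated. Writing it out, with reference to the mITT Population, would be harmless but would change no number, analysis or decision.

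The consequence of a wrong assumption is real but its size is unknown. At 71 per arm, power runs from 85.4% at 11 points to 59.2% at 8; at the 90-per-arm ceiling it runs from 92.5% to 69.5%. These rest on SD 21.6 and on assumed effects that the documents neither support nor contradict.

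Once data exist, interpretation rests on the Day 95 estimate and its interval, with half-width about 6.4 to 7.2 points under the same SD. That addresses directly whether an 11-point average is compatible with the data. The severity mix is a smaller, descriptive matter that analysts can tabulate if a screening grade is recorded. Stratum estimates would not resolve the dilution question, since the contrast has a half-width of 13.0 to 17.9 points under the assumed shares.
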